The subgenual Anterior Cingulate Cortex (sgACC) has been well established as a brain area sensitive to negative mood inductions and is implicated in neural abnormalities associated with affective and stress disorders. It is therefore one of the primary targets for deep brain stimulation (DBS) treatment of MDD using surgically implanted DBS devices. Recent posthoc imaging studies of patients who have undergone TMS treatment for depression suggest that treatment outcomes tended to be better when patients were by chance stimulated in an area of lateral prefrontal cortex that had high levels of functional connectivity with sgACC. Based on this finding, and on our own interleaved TMS/fMRI probe data, we contend that targeting delivery of TMS to the brain surface non-invasively as indicated by sgACC resting functional connectivity may be especially effective in downregulating sgACC and thereby producing superior clinical outcomes. We have used TMS/fMRI to better understand causal communication among circuits typically examined with resting fMRI alone (Chen et al., 2013). Our recent work suggests there are specific sites that, when stimulated, influence subcortical brain areas implicated in affective disorders such as the sgACC. Previously, we targeted TMS based on brain atlases mapped onto individual brain surfaces. This study will utilize individualized targeting from participants' own fMRI scans. We will focus on a target region of the lateral prefrontal cortex (LPFC) that our data suggest is particularly effective at influencing the sgACC. As alternative brain targets, we will also test the efficacy of prefrontal sites with hypothesized connections to downstream depression-related abnormalities. A normal, FDA-approved clinical application of TMS involves long trains of repetitive TMS applied for approximately 40 minutes, 5 days/week, over 2-6 weeks, for a total of 10-30 TMS visits. The present study utilizes the same FDA-approved devices (Magventure Cool-Coil B65, MagVenture X100 Stimulator) to administer TMS. We will be administering brain stimulation in smaller doses as compared with the FDA-approved protocol, but using a well-validated protocol, theta-burst stimulation (Huang et al., 2005), which will result in a reduced number of total pulses delivered to the subject in any given TMS session. This is not a treatment study, and stimulation is not designed to provide treatment in this study. Instead, the TMS delivery is meant to temporarily modify brain circuit communication between the lateral prefrontal cortex and subcortical structures to prove that this pathway can be influenced non-invasively with TMS. In addition to these repetitive TMS protocols, we will perform brief TMS delivery in the MRI machine with a research device (MRI-B91 Air Cooled Coil). We have attached several additional examples of prior studies which have safely utilized TMS outside of its FDA-approved protocol, even in heightened doses. For instance, in prior studies subjects have received the FDA-approved 3000 rTMS pulses, but done bilaterally instead of unilaterally (6000 total stimulations) every weekday over 4-6 weeks (see Bakker et al., 2015). Similarly, subjects have received 3600 rTMS pulses every weekday over 10 days (see Chistyakov et al., 2015), or 3000 rTMS pulses every weekday over 6 weeks (see O'Reardon et al., 2007). Another study applied the FDA-approved protocol in more than a double-dose, with 6800 stimulations to 1 site every weekday over 7 weeks average participation (Hadley et al., 2013). The present study utilizes many fewer stimulations than these other protocols, with each visit including a maximum of 3700 pulses. For additional information, please see Anderson et al., 2006 for demonstrations of the safety of repeated exposure to TMS. Likewise, please see Wagner et al., 2007 and Parkin et al., 2015 for reviews of the importance of TMS research and how our proposed studies fit in the present and growing body of literature.

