
Study Design

Phase*

Not applicable

Design

All subjects will receive active TMS to our novel fMRI-guided targeting method over the course of 3 days, preceded and followed by a 2hr MRI scan during which TMS is administered throughout.

Study duration

Enrollment of subjects in this study will take place over approximately 2 years. Each subject will complete 8 study visits over the course of ~3 weeks. The study schedule is as follows: Visit 1: Consenting / Screening procedures (approx. 3 hours) Visit 2: Baseline MRI Scan to determine TMS targets (1 hour) Visit 3: TMS/ fMRI Scan #1 & Assessments (approx. 3 hours) Visits 4-6: Mini TBS Visits - TMS to the fMRI-guided site (approx. 1hr each) Visit 7: Follow-Up Visit - TMS/fMRI Scan #2 (approx. 3 hours)

Resources necessary for human research protection

Describe research staff and justify that the staff are adequate in number and qualifications to conduct the research. Describe how you will ensure that all staff assisting with the research are adequately informed about the protocol and their research related duties. Please allow adequate time for the researchers to conduct and complete the research. Please confirm that there are adequate facilities for the research.

Staff will be trained on the protocol and inclusion/exclusion criteria. TMS protocols, as well as clinical and neurological assessments, will be administered by specially-trained staff in the Center for Neuromodulation in Depression and Stress the University of Pennsylvania Department of Psychiatry. All TMS staff will be trained by the PI ([name].) and the Center Director ([name].). Other facilities will include various laboratory spaces specializing in advanced computing and analysis of neuroimaging and cognitive datasets. Scans will be conducted on a Siemens Prisma 3 Tesla whole-body MRI with a 64-channel head/neck array, housed in the Center for Advanced Magnetic Resonance Imaging and Spectroscopy (CAMRIS). Additional MRI resources, such as a mock scanner, may be accessed from the Center for Functional Neuroimaging (CfN).

Characteristics of the Study Population

Target population

Patients will be diagnosed with current Major Depressive Disorder as determined by meeting the DSM criteria for MDD; a subset of patients will be diagnosed with current Persistent Depressive Disorder (PDD) instead of current MDD, as per the May 2018 protocol. They will be otherwise healthy, right-handed, adults aged 18-60 years.

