Subjects will be compensated through University of Pennsylvania supported Greenphire ClinCard. This is a reloadable prepaid card (similar to a debit/credit card) which allows funds to be available immediately. Study staff will provide participants with a ClinCard Cardholder FAQ: US document (attached). Subjects will receive compensation at the end of their study completion. If subjects do not fully complete the study, they will receive compensation for the parts of the study they did complete, based on the following outline: Visit 1: Clinical Interview (\$20.00) Visit 2: Baseline MRI Scan to determine TMS targets (\$40.00) Visit 3: Baseline TMS/MRI Scan #1 (\$60.00) Visit 4-6: TMS to the fMRI-guided site (\$70.00 each, \$210.00 total) Visit 7: Follow-up TMS/MRI Scan #2 (\$120.00) Total compensation for full study completion is \$510.00 for each subject. Subjects who do not feel comfortable with the Greenphire ClinCard may be compensated by a check, in lieu of the ClinCard. We are not stating this option in the ICF, as we would prefer all participants to use the ClinCard for consistency; however, we acknowledge that not all individuals will feel comfortable with this method and therefore, if during the consenting process or at any time during the study, a participant expresses discomfort, we will then verbally offer them the option of being paid with a check.

Study Procedures

Suicidal Ideation and Behavior

Does this research qualify as a clinical investigation that will utilize a test article (ie- drug or biological) which may carry a potential for central nervous system (CNS) effect(s)?

No

Procedures

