
The following documents are currently attached to this item:

There are no documents attached for this item.

Deception

Does your project use deception?

No

International Research

Are you conducting research outside of the United States?

No

Analysis Plan

Clinical outcome will be evaluated on symptom scales in a TMS target x Time ANOVA. Similarly, rate of change (slope) x TMS Target will indicate how rapidly each round of stimulation influences symptoms.

The following documents are currently attached to this item:

There are no documents attached for this item.

Data confidentiality

- Paper-based records will be kept in a secure location and only be accessible to personnel involved in the study.**
- Computer-based files will only be made available to personnel involved in the study through the use of access privileges and passwords.**
Prior to access to any study-related information, personnel will be required to sign statements agreeing to protect the security and confidentiality of identifiable information.
- Wherever feasible, identifiers will be removed from study-related information.**
A Certificate of Confidentiality will be obtained, because the research could place the subject at risk of criminal or civil liability or cause damage to the subject's financial standing, employability, or liability.
- A waiver of documentation of consent is being requested, because the only link between the subject and the study would be the consent document and the primary risk is a breach of confidentiality. (This is not an option for FDA-regulated research.)**
- Precautions are in place to ensure the data is secure by using passwords and encryption, because the research involves web-based surveys.**
Audio and/or video recordings will be transcribed and then destroyed to eliminate audible identification of subjects.

Subject Confidentiality

Patients entering the study will be given a unique identifying code. This code will be used on all data obtained from scans or the medical record. Everything will be immediately coded and this coded information will be stored in secure cabinets inside locked rooms or in password protected, IRB compliant online databases, such as REDCap. Any documents connecting the code with the participant name will also be stored in secure cabinets inside locked rooms or in password protected, IRB compliant online databases, such as REDCap.

Sensitive Research Information*

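### Both planned symptom analyses test a TMS target factor, but the stated design has one target and defines no second group, so the tested effects have 0 degrees of freedom

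*Combined protocol and SAP*

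**What the plan says.** The Analysis Plan consists of two sentences, and both use the target as a factor. The first reads "Clinical outcome will be evaluated on symptom scales in a TMS target x Time ANOVA". The second says that "rate of change (slope) x TMS Target will indicate how rapidly each round of stimulation influences symptoms".

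The Design section describes one group: "All subjects will receive active TMS to our novel fMRI-guided targeting method over the course of 3 days". The payment outline under Subject compensation repeats this for the stimulation days, "Visit 4-6: TMS to the fMRI-guided site", and the visit list under Study duration also names a single guided site for those visits. Accrual gives one pool of 40 usable completers, not divided by target. No section mentions randomisation, sham, a comparator or numbers per target.

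Three places suggest more than one site:
- The Background states: "As alternative brain targets, we will also test the efficacy of prefrontal sites with hypothesized connections to downstream depression-related abnormalities".
- The visit list describes Visit 2 as "Baseline MRI Scan to determine TMS targets", in the plural.
- Procedures speaks of marking stimulation sites, also in the plural, for the Visit 3 scan with concurrent TMS.

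None of these says which subjects receive another target, at which visit, or by what assignment. The Background also says: "This is not a treatment study, and stimulation is not designed to provide treatment in this study". The listed primary and secondary outcomes concern functional brain activity, not symptom scales.

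**The concern.** An interaction between target and time compares change across targets. With one target there is nothing to compare, and the model returns no estimate and no test for it. The same holds for slope by target. These are the only two analyses in the Analysis Plan, so under the stated design neither delivers the effect it is meant to test.

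Two things are at stake. First, the analyst would have to fall back on change over time in one uncontrolled group, while the plan still promises to show how fast stimulation affects symptoms. Second, if the levels of the factor stay undefined, subjects could be grouped by target after the data are seen.

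**Working it through.** **The plan's own figure.** The only sample-size figure is enrolment: 40 usable completers + 55 expected losses = 95, which reproduces. No alpha, power, effect size or SD is given.

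**Degrees of freedom.** Let k be the number of targets and T the number of symptom assessments. Target has k − 1 df, Target × Time has (k − 1)(T − 1), and slope × Target has k − 1. Procedures gives the same clinical assessments at Visits 3 and 7, so T = 2. If the brief assessments at Visits 4-6 include the same symptom scale (not stated), T = 5. The rank of the design matrix for 40 subjects confirms the formulas:

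| Targets | Time | Rank, Time only | + Target | + Target × Time | Interaction df |
|---|---|---|---|---|---|
| 1 | 2 visits | 2 | 2 | 2 | 0 |
| 1 | 5 visits | 5 | 5 | 5 | 0 |
| 1 | linear slope | 2 | 2 | 2 | 0 |
| 2 | 2 visits | 2 | 3 | 4 | 1 |
| 2 | 5 visits | 5 | 6 | 10 | 4 |

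With one target only Time can be tested: F(1, 39) for two visits, F(4, 156) for five.

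**The possible readings of the extra targets.**
- *Probe sites in the scanner at Visits 3 and 7 only.* Each subject has one symptom score per visit, whatever number of sites is probed, so target cannot be a factor for symptoms. It could be a within-subject factor for the imaging data.
- *Different subjects stimulated at different targets at Visits 4-6.* The interaction then exists, but its levels, group sizes and assignment are nowhere defined.
- *Individual coordinates under one targeting method.* No section defines these as levels of a factor.

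**Precision if there were two targets.** Assumptions: two-sided alpha 0.05, 80% power, noncentral t.
- One group, n = 40, noncentrality d√40, 39 df: d = 0.454 change-score SD.
- Two groups of 20, noncentrality d/√(1/20 + 1/20), 38 df: d = 0.909 change-score SD.

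Multiplying by √(2(1 − r)), with r an assumed pre-post correlation, converts these to single-visit SD:

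| r | One group | 20 v 20 |
|---|---|---|
| 0.5 | 0.454 | 0.909 |
| 0.7 | 0.352 | 0.704 |
| 0.8 | 0.287 | 0.575 |

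**What a Time-only test would show with no TMS effect.** This is an illustration; both drift and r are assumed. With drift δ in single-visit SD, dz = δ/√(2(1 − r)) and the noncentrality is dz√40. The probability of p < 0.05 is:

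| Drift | r = 0.5 | r = 0.7 | r = 0.8 |
|---|---|---|---|
| 0.1 SD | 0.095 | 0.125 | 0.164 |
| 0.2 SD | 0.235 | 0.357 | 0.496 |
| 0.3 SD | 0.457 | 0.666 | 0.833 |

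**The case against.** The strongest reply is that 0 df requires exactly one target level, and the text is not that firm. A common targeting method is not a common target. The guided site may mean each person's own site, and the Background does announce alternative targets. On that reading the sections are compatible but under-described, and the defect is an undefined factor. Singular and plural wording settles nothing: Procedures uses both in the same sentence.

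This narrows the claim without removing it. The 0 df result is conditional on the design as stated. On every other reading the symptom analysis still either cannot be estimated or cannot be specified from the documents.

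A second reply concerns weight. Symptom scales are not a listed outcome, the study is declared not to be a treatment study, and Time stays estimable. This is correct, and it limits the consequence to the clinical analysis. It does not rescue an Analysis Plan in which both tests fail under the stated design and one promises an inference that design cannot give.

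A third reply is that the numbers beyond the df rest on assumptions. They do. The 20/20 split is the most favourable two-group division: the detectable difference becomes 0.94 at 25/15, 1.05 at 30/10 and 1.37 change-score SD at 35/5. The drift table describes the fallback test and not the one the plan names. It shows only why the fallback cannot carry the plan's claim.

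**Conclusion.** The concern holds and must be fixed. Under the design as stated, Target × Time and slope × Target each have 0 df, whether there are two symptom assessments or five. This needs no assumption beyond one stimulated target at Visits 4-6. If several targets are in use, the interaction exists, but the plan does not define it, and 40 completers would support only a coarse comparison.

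The estimable quantity, change over time in one group, mixes any TMS effect with natural course, regression to the mean and repeated testing. It cannot support the plan's statement about how stimulation affects symptoms. The listed imaging outcomes are outside this point.

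**What to change.** Reconcile the Background, the Design and the Analysis Plan, stating which sites are stimulated, at which visits and in whom. Then:

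1. If Visits 4-6 use one guided site, remove the target factor from both symptom analyses. Fit a one-group repeated-measures model of change from Visit 3 to Visit 7, with visit fixed and participant random. With two complete visits this is equivalent to a paired t-test. Add Visits 4-6 only if the same symptom scale is collected there. Report the change with a 95% CI as descriptive, and delete the statement that the slope shows how rapidly stimulation acts on symptoms.
2. Keep a site factor only as a within-subject factor for the TMS/fMRI data, and only if more than one site is probed in each person.
3. If subjects do receive different targets at Visits 4-6, state the targets, the number of subjects per target and how they were assigned. Treat any comparison that was not randomised as exploratory.

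Options 1 and 2 cost a text change to the Analysis Plan and one clarifying sentence in the Background or Design. Option 3 requires documenting what is already in use, with no change to allocation. The price is a more modest claim about symptoms.
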